9.3 REPLACEMENT POLICY

Discontinuations after randomisation due to adverse events will not be replaced. Discontinuations after randomisation for any other reasons may be replaced at the discretion of the Sponsor, in order to reach the agreed number of evaluable subjects for pharmacokinetic endpoints.

9.4 BLINDING PROCEDURES

[figure not shown]
Not applicable as this is an open label study.

9.5 EMERGENCY UNBLINDING

Not applicable as this is an open label study

10 STUDY PROCEDURES

10.1 DESIGN SCHEMATIC

10.2 SCHEDULE OF ASSESSMENTS

PERIOD	SCREENING	TREATMENT		POST-STUDY FOLLOW-UP
Visit Number	1	2	3	4
Visit Name	Screening Period ¹	PK Day 1	PK Day 2	Post-Study Safety Follow-up ⁴
Visit Day/Duration	Up to 14 days	Day 1	Day 10	3-10 days after treatment discontinuation
Informed Consent	X			
Demographics ⁷	X			
Medical History	X			
Concomitant Medications and Procedures	X	X	X	X
Physical Examination	X			X
Vital Signs ²	X	X	X	X
12-lead ECG ²	X		X	
Urine Pregnancy Test ³	X	X	X	X
Haematology, Clinical Chemistry and screening Iron markers blood sampling ³	X		X ⁶	
Eligibility Confirmation and Randomisation	X	X ³		
Dispense Study Drug		X		
Supervised morning dosing with Ferric Maltol		X	X	
Sparse PK Blood Sampling for Iron markers, maltol/maltol glucuronide and NTBI ^{5,6}		X	X	
Issue and Review of Subject Study Dosing Diary		X	X	
Subject to Return Study Drug for Accountability			X	
Adverse Events		X	X	X

1. A subject may be retested once for screening laboratory criteria that do not meet protocol in/exclusion criteria, so long as randomisation occurs no more than 14 days from the initial screening date (if eligible based on retest results).

2. Vital Signs – supine systolic/diastolic blood pressure, pulse rate and body temperature at each visit; 12-lead ECG at Screening and Day 10 (between 1h and 4h post-dose) - machine reported routine ECG parameters (heart rate, PR interval, RR interval, QRS duration, QT interval) and overall clinical ECG interpretation will be recorded in the eCRF.

3. Eligibility central laboratory sampling/assessments must be completed at Screening (Visit 1), before the subject is randomised and before the first dose of Ferric Maltol study treatment is taken. Screening parameters to be tested will be:

Haematology: red blood cell count, haemoglobin, haematocrit, mean cell volume (MCV), mean corpuscular haemoglobin (MCH), mean corpuscular haemoglobin (MCHC), white blood cell count (total and differential (% and absolute), absolute reticulocyte count and platelet count.

Clinical Chemistry: ALT, AST, alkaline phosphatase, gamma-glutamyl transpeptidase (GGT), total bilirubin, creatinine, amylase, blood urea nitrogen (BUN), phosphorous, sodium, potassium, chloride, calcium, total cholesterol, uric acid, glucose, total protein, albumin.

Iron Markers: serum iron, transferrin, transferrin saturation (TSAT), total and unsaturated iron binding capacity (TIBC, UIBC) and ferritin.

Urine pregnancy test for female subjects of childbearing potential.

On Day 10 (Visit 3), haematology and clinical chemistry blood samples will be collected at one of the PK sampling times between 1h to 4h post dose). Female subjects of childbearing potential will undergo urine pregnancy tests pre-dose on Day 1 and Day 10 and at the Post-study visit.

4. Subjects who discontinue from the study prematurely should have final assessments conducted per Visit 4/Post-study Safety Follow Up, unless consent is withdrawn.

5. On PK study Days 1 and 10, all subjects will have baseline PK blood samples collected immediately prior to Ferric Maltol dosing (0h). Subjects will then have further PK blood samples collected at two (2) additional times between 0.5h and 6h after dosing on Days 1 and 10; the post-dose PK sample time collection windows will be 0.5-1h, 1.0-2.0h, 2.0-3.0h, 3.0-4.0h and 4.0-6.0h. Subjects will be assigned to the required post-dose PK blood sampling schedule in sequential order at the time of randomisation, based on current subject enrolment across all study sites. For each individual subject, the post-dose PK blood sampling schedule will be the same on Day 1 and Day 10. Post-dose blood samples should be collected within the time windows allocated only. N.B: For those subjects in PK Sample Schedule Group 1 (see summary table in Section 10.7.4), the PK blood samples for the 0.5-1h timepoint window should be taken at least 30 minutes before the PK blood samples for the 1-2h timepoint window on Day 1 and Day 10. Further details are provided in Section 10.7.2 and Section 10.7.4. After the required post-dose PK blood sampling is completed on Day 1 and Day 10, an individual subject can be discharged from the site, providing the Investigator has no ongoing safety concerns.

6. Iron markers to be tested from PK blood samples on Days 1 and 10 will be: serum iron, total and unsaturated iron binding capacity (TIBC, UIBC), transferrin, transferrin saturation (TSAT), ferritin and non-transferrin bound iron (NTBI).

7. A minimum of 25% of each gender and at least 3 subjects per age category (10 to 14y and 15-17yr) are to be enrolled in each Ferric Maltol dose group. Height (m) and body weight (Kg) will be measured at Screening (Visit 1) only.

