9.2 RANDOMISATION

Subjects will be registered into the study at the Screening visit and assigned a unique subject identification number in the eCRF. Subjects will be categorised during the screening process based upon their age (10 to 14 years of age and 15 to \leq 17 years of age) and their gender. Age and gender will be incorporated into the randomisation as stratification factors. This will ensure that a minimum of 25% of each gender and at least 3 children per age group (15-17 yrs and 10 to 14 yrs) are enrolled and treated in each Ferric Maltol dose group.

A final eligibility evaluation must be conducted by the Investigator/designee prior to randomisation in the eCRF system, once the results of all Screening assessments are available. No subject may begin Ferric Maltol treatment prior to being randomised in the eCRF system. The randomisation procedure (created using a computer generated random permutation procedure) will assign the subject to one of the three study treatment groups (Ferric Maltol 30 mg, 16.6 mg or 7.8 mg BID). The randomisation process will also specify which PK blood sampling schedule should be followed for an individual subject on Day 1 and Day 10, in order to ensure that the minimum of three subjects per age group and Ferric Maltol dose group have PK samples collected at each of the required time point windows (see Section 10.7.2).

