10.7.3 Urine Pregnancy Test

Females of childbearing potential only. A urine pregnancy test should be conducted at the Screening visit to assess eligibility using the test kits provided by the central laboratory. A repeat urine pregnancy test will be conducted prior to first dosing with Ferric Maltol on Day 1; the result of this test must be negative for dosing with Ferric Maltol to commence on Day 1. Repeat urine pregnancy testing will also be conducted on Day 10 and at the Post-study visit.

Full details of the required sample collection and processing procedures will be described in the study-specific Laboratory Manual.

10.7.4 Summary table of sparse PK blood sampling schedule on Day 1 and Day 10

On PK study Days 1 and 10, all subjects will have baseline (pre-dose) PK blood samples collected immediately prior to Ferric Maltol dosing (0h). Subjects will then have further PK blood samples collected at two (2) additional times between 0.5h and 6h after dosing on Days 1 and 10; within each Ferric Maltol dose group (7.8mg 16.6mg or 30mg BID), the post-dose PK sample time collection windows will be 0.5-1h, 1.0-2.0h, 2.0-3.0h, 3.0-4.0h and 4.0-6.0h. The twelve (12) subjects within each Ferric Maltol dose group will be assigned to the required post-dose PK blood sampling schedule in sequential order at the time of

randomisation, based on current subject enrolment across all study sites. This is summarised in the following table:

PK Sample Schedule Day 1 and Day 10	PK Sample Schedule Group 1 (N=3/12)	PK Sample Schedule Group 2 (N=3/12)	PK Sample Schedule Group 3 (N=3/12)	PK Sample Schedule Group 4 (N=3/12)
Pre-dose (0h)	X	X	X	X
0.5 – 1 hour	X	X		
1 – 2 hours	X		X	
2 – 3 hours		X		X
3 – 4 hours			X	
4 – 6 hours				X

For each individual subject, the post-dose PK blood sampling schedule will be the same on Day 1 and Day 10. Post-dose samples for each subject must be collected within the allocated time-windows (e.g. Between 0.5-1h or 1-2h); the exact time of sample collection will be recorded in the eCRF. For those subjects in PK Sample Schedule Group 1 (see above table), the PK blood samples for the 0.5-1h timepoint window should be taken at 30 minutes before the PK blood samples for the 1-2h timepoint window on Day 1 and Day 10, to provide an adequate spread of actual sampling times for the population PK analysis.

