5 On PK study Days 1 and 10, all subjects will have baseline PK blood samples collected immediately prior to Ferric Maltol dosing (0h). Subjects will then have further PK blood samples collected at two additional times between 0.5h and 6h after dosing on Days 1 and 10; the post-dose PK sample time collection windows will be 0.5-1h, 1.0-2.0h, 2.0-3.0h, 3.0-4.0h and 4.0-6.0h. Subjects will be assigned to the required post-dose PK blood sampling schedule in sequential order at the time of randomisation, based on current subject enrolment across all study sites. For each individual subject, the post-dose PK blood sampling schedule will be the same on Day 1 and Day 10.

6 Iron markers to be tested from PK blood samples on Days 1 and 10 will be: serum iron, total and unsaturated iron binding capacity (TIBC, UICB), transferrin, transferrin saturation (TSAT), ferritin and non-transferrin bound iron (NTBI).

7 Demographics include age, gender, ethnicity and race and are recorded at the Screening Visit; Height (m) and body weight (kg) will be measured at the Screening Visit only.

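### PK sampling schedules are assigned sequentially with no age element, so the age coverage that Protocol 9.2 says randomisation will ensure is not secured in the 3–4 h and 4–6 h windows

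*Protocol*

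**What the plan says.** Protocol 9.2 stratifies the dose randomisation by age (10–14 and 15–17 years) and gender, and adds: "The randomisation process will also specify which PK blood sampling schedule should be followed for an individual subject on Day 1 and Day 10". Its stated purpose is that a "minimum of three subjects per age group and Ferric Maltol dose group have PK samples collected at each of the required time point windows".

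The rule that sites and the eCRF would follow is given elsewhere. Protocol 10.2 footnote 5 reads: "Subjects will be assigned to the required post-dose PK blood sampling schedule in sequential order at the time of randomisation, based on current subject enrolment". Protocol 10.7.4 places the sequence inside the dose group: "The twelve (12) subjects within each Ferric Maltol dose group will be assigned to the required post-dose PK blood sampling schedule in sequential order". SAP Table 2 footnote 5 repeats the rule ("in sequential order at the time of randomisation, based on current subject enrolment across all study sites"), as does SAP 4.2.1. Age appears in none of these four places.

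The table in Protocol 10.7.4 defines four schedules with 3 of 12 children each. Only schedule 3 samples at 3–4 h and only schedule 4 at 4–6 h. On repeat sampling, footnote 5 says: "For each individual subject, the post-dose PK blood sampling schedule will be the same on Day 1 and Day 10".

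**The concern.** Protocol 9.2 makes age coverage of the windows an aim of the allocation, but the allocation rule contains nothing that would produce it. Which children supply the late samples then depends on order of arrival within a dose group. With three children per late cell, all three can easily come from one age band. Because the schedule is carried over from Day 1 to Day 10, any imbalance recurs on both PK days.

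The by-time descriptive statistics for maltol, maltol glucuronide, serum iron and TSAT sit within the primary endpoints (Protocol 6.3). SAP 8.4 summarises and plots them by dose group, visit and nominal time range. Doses are fixed in mg across ages 10 to 17, with a broad range of weights expected (Protocol 5.5), so exposure may well differ by age. In a single-age late cell, the early-to-late change in that dose group's means is partly a comparison of younger with older children. The study is meant to inform dose choice for a Phase 3 paediatric study, so readers will look closely at these by-dose profiles.

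**Working it through.** **Inputs.** 36 children, 12 per dose group (Protocol 7.1). Four schedules of 3 children, two post-dose samples each per PK day (10.7.4). At least 3 children per age band per dose group (10.2 footnote 7), so permitted splits run from 3:9 to 9:3. Assumptions: arrival order is unrelated to age, and the split is the same in all three dose groups.

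**Step 1: children per window.** The schedules cover {0.5–1, 1–2}, {0.5–1, 2–3}, {1–2, 3–4} and {2–3, 4–6} h. With 3 children each, the five windows hold 6, 6, 6, 3 and 3 children, or 24 = 12 × 2 sample slots per dose group.

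**Step 2: the plan's own figure, a minimum of three.** Read literally, as three per age band within each dose group, every window needs 3 × 2 = 6 children. That is 6 × 5 = 30 slots against 24, and the two late windows have 3 children where 6 are needed. It would take 15/2, rounded up to 8, children per age band: 16 per dose group and 48 in all. A looser reading is three per dose group and, separately, three per age band pooled over doses. The first part is then met exactly. The second is possible but not assured (last column below).

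**Step 3: one late cell.** With a children in one band, P(single-age) = [C(a,3) + C(12−a,3)] / C(12,3).
- 6:6: (20 + 20)/220 = 18%
- 5:7: (10 + 35)/220 = 20%
- 4:8: (4 + 56)/220 = 27%
- 3:9: (1 + 84)/220 = 39%

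**Step 4: two late cells in a dose group, six in the trial.** The two late cells are disjoint sets of three, so P(at least one) = 2p − P(both).
- 6:6: 0.3636 − 0.0455 = 0.318. Over three dose groups, 1 − (1 − 0.318)³ = 0.683.
- 3:9: 0.7727 − 0.1000 = 0.6727. Over three dose groups, 1 − 0.3273³ = 0.9649.

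**Step 5: pooled over doses.** A late window then holds nine children. P(all one band) is 2 × (20/220)³ = 0.15% at 6:6 and (84/220)³ + (1/220)³ = 5.6% at 3:9.

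| Split | One late cell single-age | At least one of 2 in a dose group | At least one of 6 | Expected of 6 | Pooled window all one band | Pooled window at least 3 of each band |
|---|---|---|---|---|---|---|
| 6:6 | 18% | 32% | 68% | 1.1 | 0.15% | 87% |
| 5:7 | 20% | 36% | 74% | 1.2 | 0.4% | 81% |
| 4:8 | 27% | 49% | 87% | 1.6 | 1.7% | 64% |
| 3:9 | 39% | 67% | 96% | 2.3 | 5.6% | 40% |

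**The case against.** The case against has several parts.

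- **Age is not ignored.** Protocol 9.2 names age coverage as a purpose, and no passage expressly says that the sequence disregards age band. This stands as a limit: the probabilities describe the rule as written. If the eCRF list does run within age band, the documents should say so.
- **The primary analysis is protected.** A reader might infer that age and sampling time are confounded throughout the PK analysis. The documents do not support that. Population models use exact sampling times, which are recorded. Each child on schedules 3 and 4 also gives a pre-dose and an earlier post-dose sample. Age and body weight are candidate covariates (SAP 8.5.3). If doses are modelled together, nine children inform each late window. This part stands.
- **Half-life does not rest on late samples alone.** Adult half-lives were 0.8 h (maltol) and 1.1 h (glucuronide) (Protocol 12.1), so the 1–2 h and 2–3 h windows, six children each per dose group, also inform the decline. This stands.
- **Predictability.** A reader might infer selection bias from a sequential order. The study is open label, but dose is revealed at the same step and the sequence runs across all sites, so a site cannot readily foresee the next schedule. No route to bias is shown.
- **A 2:1 cell still cannot separate age from time.** True within one cell. Mixing removes the extreme case and makes early and late cells more alike in age; it does not support an age comparison in three children.
- **Timing.** SAP 4.2.1 already describes assignment in the past tense, and SAP 7.1 lists each child's age stratum, dose and PK sampling group. A change to allocation may come too late, but the listing is not a summary that readers of SAP 8.4 would see.

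**Conclusion.** The point holds as a property that the protocol states and its own allocation rule does not deliver. Followed as written, the rule leaves a given late dose-by-window cell single-age in 18% to 39% of cases, always fewer than half. At least one of the six is single-age in 68% to 96% of trials, with 1.1 to 2.3 expected. These figures rest on 12 children per dose group, the same age split in each, and arrival unrelated to age. Recruitment clustered by age would raise them.

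The effect falls on the by-dose, by-window summaries and on how precisely a late-phase age effect can be estimated. It does not reach as far as a population PK analysis in which age cannot be told from time, nor to any bias from foreseeable allocation. Separately, the literal 9.2 minimum is impossible in a three-child window, whatever rule is used.

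**What to change.** **If allocation is still open.** In Protocol 10.2 footnote 5 and 10.7.4, and in SAP Table 2 footnote 5 and 4.2.1, replace the sequential rule with assignment by dose group and age band, held to exactly three children per schedule per dose group. One way is a single 12-slot list per dose group, with schedules in the order 3, 4, 1, 2, 3, 4, 1, 2, 1, 2, 3, 4. One age band fills from the front and the other from the back. Each schedule occurs three times. Schedule 3 sits in slots 1, 5 and 11, and schedule 4 in slots 2, 6 and 12. With at least three children from each end, both late windows therefore contain both bands at every split from 3:9 to 9:3, and the split need not be known in advance. The first three slots (3, 4, 1) and the last three (2, 3, 4) each touch all five windows, so the earlier windows are mixed too.

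Rotating independently within each band is not enough. At 6:6 each band gives two of the four schedules a second child. If those are chosen at random, a given late window drops to two children with probability ½ × ½ = 25%, and at least one of the two does so with probability 0.50 − (1/6)² = 47%.

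**In either case.** Reconcile Protocol 9.2 with 10.7.4 by restating the minimum as what the design delivers. With the list above, that is at least three children per dose group in every window, with both age bands represented.

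**If enrolment is complete.** Add to SAP 8.4 a count of children per window by dose and age band, and state that early-to-late differences in single-age cells will not be read as time effects alone.

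**Cost.** A revised central allocation list and a sentence or two in each document, or one extra table. No additional children or samples.

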10.3 DEMOGRAPHICS AND MEDICAL HISTORY

The following will be documented at Screening and updated (if required) prior to randomisation: Date of Birth, race and ethnicity, gender, all current medical conditions, all medical history relevant to iron deficiency diagnosis regardless of onset, all clinically significant medical history from the past 5 years including all malignancies, sterilisations, hospitalisations and surgeries; the method of contraception for female subjects of childbearing potential, if applicable. Body weight (Kg), height (m) will be measured at the Screening visit only.

10.4 PHYSICAL EXAMINATION

A brief physical examination is to be conducted to assess safety. The examination should include an assessment of general appearance, skin, head, eyes, ears, nose and throat, cardiovascular, respiratory, abdominal, gastrointestinal and musculoskeletal systems.

10.5 CONCOMITANT MEDICATIONS AND PROCEDURES

The following will be documented at Screening and updated (if required) prior to randomisation: all current medications at the time of Screening or stopped within 3 months of screening and any medical procedure performed within 3 months prior to Screening.

The following will be documented throughout the study: any medications initiated, stopped or with dose and/or frequency changes throughout the study. Any medical procedure performed throughout the study.

Medical procedures to be documented are any therapeutic intervention such as surgery/biopsy, physical therapy or diagnostic assessment (e.g. blood gas measurement).

10.6 VITAL SIGNS AND 12-LEAD ECG

Body temperature (°C), blood pressure and pulse rate will be assessed at Screening, pre-dose on Days 1 and 10 and at Post-study; blood pressure and pulse rate should be measured after the subject has been supine for at least 5 minutes.

A 12-lead ECG will be recorded at Screening and again on Day 10 (between 1h and 4h post-dose). Machine reported standard ECG parameters (heart rate, PR interval, RR interval, QRS duration, QT interval) and overall clinical ECG interpretation will be recorded in the eCRF.

10.7 LABORATORY ASSESSMENTS

10.7.1 Haematology and Clinical Chemistry

Routine clinical laboratory safety bloods for haematology (1mL) and clinical chemistry/iron markers (5mL) evaluations will be collected at Screening to assess eligibility. Haematology (1mL) and clinical chemistry (2.5mL) will be repeated on Day 10 (at one of the PK sampling times between 1h to 4h post dose). Additional testing may be required if any abnormal value is reported and this must be followed until it is resolved (other than iron indices and low

haemoglobin due to ongoing iron deficiency/anaemia, or abnormal results due to other pre-existing conditions).

All analyses will be conducted by a central laboratory. Procedures for the collection, processing, storing, and transporting of samples to the laboratory will be fully described in the study-specific Laboratory Manual.

Investigators will review, sign and date all lab results upon receipt from the central laboratory. If a value is flagged as outside of the normal range, the Investigator must document the abnormality as 'clinically significant' (CS) or 'non-clinically significant' (NCS). Any lab abnormality assessed as 'CS' must be recorded as an AE if not explained by a pre-existing condition (documented in the medical history).

The signed paper copy of the laboratory report is retained at the investigational site. The electronic data transferred from the central laboratory database to the clinical study database will be considered source data for the derivation of summary data and listings presented in the clinical study report.

10.7.1.1 Haematology test parameters

Red blood cell count, haemoglobin, haematocrit, mean cell volume (MCV), mean corpuscular haemoglobin (MCH), mean corpuscular haemoglobin (MCHC), white blood cell count (total and differential (% and absolute), absolute reticulocyte count and platelet count.

10.7.1.2 Clinical Chemistry and Screening Iron Markers test parameters

Clinical Chemistry: ALT, AST, alkaline phosphatase, gamma-glutamyl transpeptidase (GGT), total bilirubin, creatinine, amylase, blood urea nitrogen (BUN), phosphorous, sodium, potassium, chloride, calcium, total cholesterol, uric acid, glucose, total protein, albumin.

Iron Markers: serum iron, transferrin, transferrin saturation (TSAT), total and unsaturated iron binding capacity (TIBC, UIBC) and ferritin.

10.7.2 Pharmacokinetics

Blood samples for maltol and maltol glucuronide on Day 1 and Day 2 (Visits 2 and 3)

3mL venous blood samples will be collected in lithium-heparin tubes by indwelling cannula or venepuncture at the required times on the PK assessment days (Days 1 & 10), relative to the time of Ferric Maltol morning dosing: pre-dose then two further times between 0.5-6 hours post-dose (see Section 10.7.4).

Following collection and mixing, blood samples will be centrifuged and the resultant plasma samples separated and stored at -20°C at the study site, prior to collection and onward shipping to the central laboratory on dry ice for subsequent assay of maltol and maltol glucuronide plasma concentrations using appropriately validated bioanalytical methods. Full details of the required sample collection, processing and handling logistics will be specified in

the study specific Laboratory Manual. Samples will be destroyed at the end of the study, once all analyses are complete.

Blood samples for iron markers and Non-Transferrin Bound Iron (NTBI) on Day 1 and Day 10 (Visits 2 and 3)

5mL venous blood samples will be collected in serum separator tubes (SST) by indwelling cannula or venepuncture at the following times on the PK assessment days (Days 1 & 10), relative to the time of Ferric Maltol dosing: pre-dose then then two further times between 0.5-6 hours post-dose (same times as blood samples for maltol/maltol glucuronide for each individual, see Section 10.7.4).

Following collection and mixing, blood samples will be centrifuged and the resultant serum samples separated and split into 1 primary (ambient) and 2 frozen (-20°C) aliquots at each timepoint. Ambient serum samples will be shipped to the central laboratory for subsequent assay of serum iron, transferrin, transferrin saturation (TSAT), total and unsaturated iron binding capacity (TIBC, UIBC) and ferritin. Frozen serum aliquots will be stored at site for later onward shipping on dry ice to the central laboratory. One (1) aliquot of frozen serum from each sampling timepoint on Day 1 and Day 10 will be assayed for serum concentrations of NTBI using an appropriately validated method; the second serum aliquot per timepoint will be stored as a backup sample at the central laboratory. Full details of the required sample collection, processing and handling logistics will be specified in the study specific Laboratory Manual. Samples will be destroyed at the end of the study, once all analyses are complete.

